4.3.16 Far Best Corrected Visual Acuity (FBCVA)

FBCVA will be calculated in Log Mar as: $\text{Log}_{10} (10 / \text{Visual acuity})$.

4.3.17 Adverse event (AE) time to occurrence

Time to AE occurrence (days) will be calculated as follows:

Date of onset – Date of IP first instillation.

4.3.18 AE duration

Duration (days) of an AE will be calculated as follows:

(Date of recovery – Date of onset) + 1.

5 DESCRIPTION OF THE STUDY POPULATION

5.1 Disposition of patients

The number of enrolled patients will be presented. The number (%) of patients included in each analysis set (Safety, mITT and PP sets) will be presented. The number (%) of patients by centre will be presented for each analysis set.

The number (%) of patients per visit as considered in the analysis will be described on the Safety set, on the mITT set and for the PP set.

The number (%) of patients who prematurely discontinued the study and the primary reason for discontinuation will be presented on the Safety set and on the mITT set. A listing will be performed presenting the patients who prematurely discontinued the study with the detailed reason for discontinuation.

The number (%) of patients with at least one major deviation, the number (%) of patients with only minor deviations (without major deviations) and the number (%) of patients with minor deviations (including those with major deviations) will be presented on the mITT set. The reasons for deviation will be also described on the mITT sets and an individual patient data listing with all minor/major deviations will be provided.

A listing of all the patients including information about populations and reason for exclusion, worse eye, will be performed on the enrolled patients' population.

A listing of visits as considered in the analysis will be performed on the enrolled patient's population.

5.2 Demographics and baseline characteristics

The demographics and baseline characteristics of the patients will be described by centre on the mITT set and on the Safety set.

The following characteristics will be summarised:

- Demographic characteristics:
 - Age (years) as continuous and in classes (<65, ≥65 years old),
 - Gender,
 - Gender by age class (<65, ≥65 years old),
- Medical history (*)
 - Ocular medical and surgical history other than the studied disease.
 - Systemic medical history.
- Surgical history (*)
 - Ocular surgical history related to another disease than DED.
 - Systemic surgical history.

(*) Diagnoses (for medical history) and surgical procedures (for surgical history) will be coded using the Medicinal Dictionary for Regulatory Activities (MedDRA) version 21.1, September 2018 (English).

- Number (%) of patients will be presented by System Organ Class (SOC) and Preferred Term (PT). Ocular treatments (**)
 - Previous ocular treatments,
 - Concomitant ocular treatments.
- Non-ocular treatments (**)
 - Previous non-ocular treatments,
 - Concomitant non-ocular treatments.

(**) All previous and concomitant ocular and non-ocular treatments will be coded using the World Health Organisation-Drug Dictionary (WHO-DD Format C March 2017).

Treatments will be summarised according to the Anatomical therapeutic chemical (ATC) class (level 2 and level 4) of the WHO-DD dictionary. A previous treatment will be defined as a treatment stopped prior to (or the same day as) the first instillation of the IP. A concomitant treatment will be defined as a treatment i) started after (or the same day as) the first instillation of the IP, ii) started prior to and continued after the first instillation of the IP. If the classification is not possible due to partial start/end date(s) of treatment, the treatment will be considered as concomitant.

- History of Dry eye,
 - Localisation (Right / Left / Both),
 - Time since DED diagnosis (months),
 - Known Dry eye requiring artificial tears within the last three months (Yes / No),
 - Origin of Dry eye (Primary Sjögren syndrome / Secondary Sjögren syndrome / Meibomian gland deficiency / Non Sjögren aqueous deficiency / Other).

Data regarding contraception status will be presented in an individual data listing.

Values before first IP intake of the efficacy and safety endpoints will be provided in statistical tables with assessments at Visit 3 (D14) and Visit 4 (D42) (see Section 6).

5.3 Treatment exposure and compliance

The following data on the use of Physiol and IP will be summarised on the Safety and mITT sets:

- Physiol: duration of physiol (days),
- Treated eye(s) by IP (Right / Left / Both),
- Duration of IP (days),
- IP Mean daily dose regimen at Visit 3 (D14) and Visit 4 (D42) and in classes.

6 EFFICACY ANALYSIS

Primary efficacy endpoint will be primarily analysed on the mITT set. Sensitivity analyses will be also performed on the PP set. Secondary efficacy endpoints will be analysed on the mITT set and on the PP set, if difference of number of patients between PP and mITT sets is more than 10%.

6.1 Primary efficacy endpoint

The primary efficacy criterion is the change in ocular symptomatology assessed on a VAS between D1 and D42.

Descriptive statistics will be performed at each assessment time (Screening, Baseline, D14 and D42) overall and by centre. Change from baseline will be described as well.

6.1.1 Main analysis of the primary efficacy endpoint

To assess the efficacy of T2769, on change in ocular symptomatology assessed on a VAS between D1 and D42, estimate of the change and associated 95% CI will be provided, as well as p-value for the paired t-test on the mITT set. Based on the LOCF method, missing values will be replaced by the last available value.

The syntax with SAS using the UNIVARIATE procedure is detailed in APPENDIX 1.

6.1.2 Sensitivity analysis of the primary efficacy endpoint

Sensitivity analysis will be performed without replacement of missing values on the mITT and PP sets.

6.1.3 Secondary analysis on the primary efficacy endpoint

Secondary analysis will be performed on the primary efficacy endpoint to test centre effect. The change from baseline at D42 will be analysed using an ANOVA including centre as covariate. The adjusted mean by centre and their corresponding 95% CI will be estimated in this model.

This analysis will be performed based on the LOCF method on the mITT set and on the observed data on the PP set.

The syntax with SAS using the MIXED procedure is detailed in APPENDIX 1.

6.2 Secondary efficacy endpoints

Secondary performance endpoints will be analysed based on the LOCF method on the mITT set and on the observed data on the PP set (if difference of number of patients between PP and mITT sets is more than 10%).

6.2.1 Global ocular staining at D42

The Oxford 0-5 grading scheme assesses the staining in three zones: temporal bulbar conjunctiva, corneal area and nasal bulbar conjunctiva.

The score of each zone (ranging from 0 to 5) will be described at each assessment time (Screening, Baseline, D14 and D42) by worse eye and the contralateral eye separately, by frequency distribution.

Global ocular staining will be also described at each assessment time (Screening, Baseline, D14 and D42) by worse and contralateral eye separately. Change from baseline will be described as well.

Evolution of Global ocular staining will be analysed using paired t-test between D1 and D42 as for symptomatology assessment on the VAS at D42 (see Section 6.1.1) by worse and contralateral eye separately.

6.2.2 Van Bijsterveld score at D42

The corneo-conjunctival exposed surface is separated in three parts: nasal bulbar conjunctive, corneal area, and temporal bulbar conjunctive.

The score of each part (ranging from 0 to 3) will be described at each assessment time (Screening, Baseline, D14 and D42) by worse eye and the contralateral eye separately, by frequency distribution.

Van Bijsterveld score will be described at each assessment time (Screening, Baseline, D14 and D42) by worse and contralateral eye separately. Change from baseline will be described as well.

Evolution of Van Bijsterveld score will be analysed using paired t-test between D1 and D42 as for symptomatology assessment on the VAS at D42 (see Section 6.1.1), by worse and contralateral eye separately.

6.2.3 Soothing sensation at D42

The soothing sensation (None / Mild / Moderate / Important) will be assessed in global for both eyes at D42.

6.3 Other efficacy endpoints

Other endpoints will be analysed based on the LOCF method on the mITT set and on the observed data one the PP set (if difference of number of patients between PP and mITT sets is more than 10%).

6.3.1 Symptomatology evaluation at D14

Evolution of the ocular symptomatology will be analysed using paired t-test between D1 and D14 as for symptomatology assessment at D42 (see Section 6.1.1).

6.3.2 Global ocular staining at D14

Evolution of Global ocular staining will be analysed using paired t-test between D1 and D14 as for symptomatology assessment at D42 (see Section 6.1.1) by worse and contralateral eye separately.

6.3.3 Van Bijsterveld score at D14

Evolution of will be analysed using paired t-test between D1 and D14 as for symptomatology assessment at D42 (see Section 6.1.1) by worse and contralateral eye separately.

6.3.4 Soothing sensation at D14

The soothing sensation (None / Mild / Moderate / Important) will be assessed in global for both eyes at D14.

6.3.5 OSDI score

The OSDI score, ranging from 1 to 100 will be described at each assessment time (Baseline, D14 and D42). Frequency distribution of OSDI score (none, mild, moderate, severe then <18 , ≥18) will be also presented at each assessment time (Baseline, D14 and D42).

Evolution of OSDI score will be analysed using paired t-test between D1 and D14 and between D1 and D42 as for symptomatology assessment on the VAS at D42 (see Section 6.1.1).

6.3.6 Ocular symptoms

Ocular symptoms (burning/irritation, stinging/eye pain, itching/pruritus, eye dryness feeling, foreign body sensation, tearing, light sensitivity) are assessed using a 4-point ordinal scale from 0 to 3, 0 indicating no symptom and 3 indicating very disturbing symptoms.

Frequency distribution of each symptom will be presented at each assessment time (Screening, Baseline, D14 and D42). In addition, frequency distribution of change from baseline in classes will be presented for each symptom at D14 and D42. Following categories will be defined: i) improvement (i.e. decrease of symptom score from baseline), absence stable, presence stable, worsening (i.e. increase of symptom score from baseline), ii) improvement, no change, worsening.

The total score of the seven symptoms, ranging from 0 to 21, will be calculated and presented for Screening, Baseline, D14 and D42. Change in total score from baseline will be also described D14 and D42.

Evolution of total score will be analysed using paired t-test between D1 and D14 and between D1 and D42 as for symptomatology assessment at D42 (see Section 6.1.1).

Data relative to other symptoms will be provided in an individual patient data listing. Other symptoms will be coded using MedDRA 21.1, September 2018 (English).

6.3.7 Conjunctival hyperaemia

Conjunctival hyperaemia will be assessed using the McMonnies photographic 6-point ordinal scale from 0 to 5. Frequency distribution will be presented at each assessment time (Screening, Baseline, D14 and D42), by worse and contralateral eye separately.

In addition, frequency distribution of change from baseline in classes will be presented for conjunctival hyperaemia at D14 and D42 on the worse eye and the contralateral eye. Following categories will be defined: i) improvement (i.e. decrease of symptom score from baseline), absence stable, presence stable, worsening (i.e. increase of symptom score from baseline), ii) improvement, no change, worsening, iii) improvement of more than 1 point (i.e. change from baseline < -1 , no significant change (i.e. change from baseline ≥ -1 and ≤ 1), worsening of more than 1 point (i.e. change from baseline > 1).

6.3.8 Schirmer test

The Schirmer test will be described at each assessment time (Baseline, D14 and D42) by worse and contralateral eye separately. Frequency distribution of Schirmer test in classes (<5 , ≥ 5 and <10 , ≥ 10 mm/5 minutes) will be also presented at each assessment time (Baseline, D14 and D42).

Evolution of schirmer test will be analysed using paired t-test between D1 and D14 and between D1 and D42 as for symptomatology assessment at D42 (see Section 6.1.1), by worse and contralateral eye separately.

6.3.9 TBUT

TBUT mean will be described at each assessment time (Screening, Baseline, D14 and D42) by worse and contralateral eye separately. Frequency distribution of TBUT in classes (<5 , ≥ 5 and ≤ 10 , > 10 seconds) will be also presented at each assessment time (Baseline, D14 and D42).

Evolution of TBUT mean will be analysed using paired t-test between D1 and D14 and between D1 and D42 as for symptomatology assessment at D42 (see Section 6.1.1), by worse and contralateral eye separately.

6.3.10 Ocular efficacy assessment by the investigator

Global judgment of efficacy by investigator assessed on a 4-point ordinal scale (Very satisfactory / Satisfactory / Not very satisfactory / Unsatisfactory) will be presented by frequency distribution for each modality and frequency distribution after regrouping 'very satisfactory' with 'satisfactory', and 'not very satisfactory' with 'unsatisfactory', at D14 and D42.

7 SAFETY ANALYSIS

Safety endpoints will be analysed on the Safety set.

7.1 Ocular symptoms upon instillation

Ocular symptoms upon instillation (burning/irritation, stinging/eye pain, itching/pruritus, eye dryness feeling, foreign body sensation) are assessed using a 4-point ordinal scale from 0 to 3, 0 indicating no symptom and 3 indicating very disturbing symptoms.

Frequency distribution of each symptom will be presented at each assessment time (D14 and D42).

The duration (minutes) and the frequency will be described by symptom on the subgroup of patients presenting with the symptom (i.e. with severity ≥ 1).

The total score of the five symptoms, ranging from 0 to 15, will be calculated and presented for D14 and D42.

Data relative to other symptoms will be provided in an individual patient data listing. Other symptoms will be coded using MedDRA 21.1, September 2018 (English).

7.2 FBCVA

FBCVA will be summarised at screening visit and D42 using usual descriptive statistics for continuous variable, in Log Mar. Frequency distribution in classes (i.e., values from 1/10 to 10/10 and $> 10/10$, with non-integer numbers rounded to the nearest integer) will be also presented.

FBCVA will be presented by worse and contralateral eye separately.

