9.1.2 Far best-corrected visual acuity in both eye

Far Best-corrected visual acuity will be measured at the screening visit (visit #1) and on Day 42 visits with the patient's best correction using a Snellen chart.

The value at screening visit will be the baseline value.

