12.3.3 Safety Analyses

Safety endpoints will be analysed in the Safety Set.

Safety analysis will be based on the following criteria:

- Ocular symptoms upon instillation: : burning/irritation, stinging/eye pain, itching/pruritus, eye dryness feeling, foreign body sensation, and other symptoms will be graded by the patient.at D14 and D42
- Far best corrected visual acuity assessment at D42
- Global ocular tolerance assessed by the investigator at D42
- Global ocular tolerance assessed by the patient at D42
- Ocular and systemic adverse events (AE)

The adverse events will be coded using the MedDRA dictionary and described according to MedDRA Preferred Term (PT) and primary System Organ Class (SOC).

The number and percentage of patients with at least one adverse event will be summarized for all AEs, study product-related AEs, serious AEs, and AEs leading to study withdrawal.

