1.3.4 Safety endpoints

Safety assessment criteria are:

- Ocular symptoms upon instillation including burning/irritation, stinging/eye pain, itching/pruritus, eye dryness feeling, foreign body sensation, and other symptoms graded by the patient after 14 days and 42 days of treatment with the T2769
- Far best corrected visual acuity (FBCVA) after 42 days of treatment with the T2769,
- Ocular tolerance assessment by the investigator after 42 days of treatment with the T2769,
- Ocular tolerance assessment by the patient after 42 days of treatment with the T2769,

- Ocular and Systemic Adverse Events (AEs) recorded throughout the investigation by the investigator.

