4.3.1 Baseline

Baseline will be defined for each assessment as an evaluation before the first instillation of the IP.

- For FBCVA, value recorded at Screening visit will be the baseline
- For others parameters, value recorded at Day 1, will be the baseline

Baseline value will be the one in the concerned eye for endpoints assessed/analysed by eye.

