4.3.6 Change from baseline

Change from baseline will be calculated as the difference:
Assessment at the visit – Assessment at baseline.

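### Visual acuity is summarised only as separate screening and D42 distributions, so losses in individual eyes can be masked although a baseline and paired values exist

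*SAP*

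**What the plan says.** FBCVA is a safety criterion in both documents: "Far best corrected visual acuity assessment at D42" (Protocol 12.3.3) and "Far best corrected visual acuity (FBCVA) after 42 days of treatment with the T2769" (SAP 1.3.4). Protocol 9.1.2 sets the timing, "Far Best-corrected visual acuity will be measured at the screening visit (visit #1) and on Day 42 visits", and adds "The value at screening visit will be the baseline value". SAP 4.3.1 agrees: "For FBCVA, value recorded at Screening visit will be the baseline". SAP 4.3.6 defines change generically as "Assessment at the visit – Assessment at baseline".

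SAP 7.2 then plans two things, for the worse and contralateral eye separately:

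- "FBCVA will be summarised at screening visit and D42 using usual descriptive statistics for continuous variable, in Log Mar";
- a frequency distribution in tenths classes from 1/10 to 10/10 and above 10/10, "with non-integer numbers rounded to the nearest integer".

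The matching outputs in SAP Appendix 2 are Tables 5.7 and 5.8, whose titles announce a summary of FBCVA and nothing on change. No listing of FBCVA values appears. By contrast, VAS (Table 4.1), Oxford (4.11), Van Bijsterveld (4.21), OSDI (4.34), Schirmer (4.57) and TBUT (4.63) each have a table whose title includes change from baseline, and hyperaemia has change in classes (4.53).

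**The concern.** Loss of vision matters eye by eye. A baseline is named for FBCVA and each eye should have one value before treatment and one at D42, but the planned analysis never links the two. Means, quantiles and class counts at each visit depend only on the set of values at that visit, not on which patient contributed which value. Gains in some eyes can therefore offset losses in others, and a report that follows the SAP exactly could describe acuity as unchanged when several eyes had worsened.

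A second, smaller issue is that the two distributions may not describe the same patients. The SAP specifies LOCF for the mITT set, while FBCVA is analysed on the Safety set. In any case there is no FBCVA measurement between screening and D42 to carry forward. SAP 4.1 also leaves out a last visit recorded more than 24 hours after the last instillation. A patient who stops treatment and is examined later would count at screening but not at D42.

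**Working it through.** The plan gives no numerical target for FBCVA, so there is no figure of its own to reproduce here. Its one design calculation (power 0.910) concerns the VAS and does not bear on this point.

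**Inputs.** From the documents: logMAR = log10(10 / acuity in tenths) (SAP 4.3.16); 50 evaluable patients (SAP 1.5); the Wilson formula (SAP 3). Assumed for illustration: the acuities, the 0.1 and 0.3 logMAR losses, and visit SDs of 0.10 to 0.20.

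**Step 1. Can the planned outputs miss losses altogether?** Take 50 eyes, one per patient: five each at 4/10, 5/10, 6/10 and 7/10, and ten each at 8/10, 9/10 and 10/10.

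- Scenario A: nobody changes.
- Scenario B: five eyes go from 10/10 to 7/10 and five from 7/10 to 10/10.

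The D42 mean in both is (5 × 1.0757 + 10 × 0.1427)/50 = 6.805/50 = 0.136. Here 1.0757 is the sum of the logMAR values for 4/10 to 7/10, and 0.1427 the sum for 8/10 to 10/10.

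| | A | B |
|---|---|---|
| **Planned in SAP 7.2** | | |
| D42 mean (SD) | 0.136 (0.128) | 0.136 (0.128) |
| D42 median; min; max | 0.097; 0; 0.398 | 0.097; 0; 0.398 |
| D42 counts, 4/10 to 10/10 | 5, 5, 5, 5, 10, 10, 10 | 5, 5, 5, 5, 10, 10, 10 |
| **Within-eye, not planned** | | |
| Mean change (SD) | 0 (0) | 0 (0.070) |
| Largest loss | 0 | log10(10/7) = 0.155 |
| Loss of 0.1 or more | 0/50 | 5/50 (10%) |
| Wilson 95% CI | 0% to 7.1% | 4.3% to 21.4% |

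The Wilson limits for 5/50 are [10 + 3.84 ± 1.96 × √(3.84 + 18)] / [2 × 53.84] = (13.84 ± 9.16)/107.68. The quartiles and the CI of the mean also agree between A and B, because the D42 values are the same set.

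**Step 2. How sensitive is the visit mean when nothing offsets the losses?** If k of 50 eyes each lose 0.3 logMAR and the rest are unchanged, the mean moves by 0.3k/50:

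- k = 1: 0.006
- k = 2: 0.012
- k = 3: 0.018
- k = 5: 0.030

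The 95% CI half-width of a single-visit mean, t(0.975; 49) × SD/√50, is 0.028, 0.043 and 0.057 for SDs of 0.10, 0.15 and 0.20. Up to three such losses stay inside the interval throughout this range. Five stay inside it at SD 0.15 or 0.20 and just exceed it at SD 0.10.

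**Step 3. Does the class table catch what the mean misses?** Often, yes. Let one eye fall from 10/10 to 5/10 (0.301) and three rise from 8/10 to 10/10 (0.097 each). The net sum is only 0.301 − 0.291 = 0.010 logMAR, but the counts move: 5/10 gains one, 8/10 loses three, 10/10 gains two. Leaving every planned output unchanged requires offsetting moves between the same classes, as in Step 1.

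**The case against.** **The tables show more than the mean.** This stands in part. SAP 3 requires quartiles, minimum, maximum and missing counts, and 7.2 adds classes. Acuity of 2/10 or less is excluded at entry, so a 1/10 at D42 would stand out. A reader might infer that losses are bound to be invisible in Tables 5.7 and 5.8. The documents do not support that, as Step 3 shows. Even a visible shift in counts, however, does not say which eyes worsened, or by how much.

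**Adverse event reporting covers it.** The protocol's definition includes worsening of a sign, and SAP 7.5.3 lists events patient by patient. But no acuity threshold makes a loss an event, and the listing carries no acuity values. The route is real but incomplete.

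**SAP 3 already compares quantitative parameters between visits by paired t-test.** This could be read as reaching FBCVA, but neither 7.2 nor the table list applies it there. It would also yield only a mean change, which is zero in Scenario B.

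**Missing data are disclosed.** Correct: missing counts are tabulated, the final-visit assessments include FBCVA at withdrawal, and investigators must try to obtain them. Disclosure does not put the two summaries on the same patients.

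**No commitment is broken.** Also correct. The protocol promises an assessment at D42 in an open pilot study, and 7.2 delivers one. A reader might infer that the SAP departs from the protocol; it does not. The point concerns the choice of analysis.

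**Conclusion.** The point holds as one of analysis choice: for a paired safety endpoint with a named baseline, SAP 7.2 and Tables 5.7 and 5.8 plan only two separate distributions, and these can mask losses in individual eyes. In the constructed case a 10% rate of eyes losing 0.155 logMAR leaves every planned output unchanged. That case rests on assumed acuities and exactly offsetting moves. It shows what can happen and does not estimate how often. Large or one-directional losses may still be noticed. Sample size, power and the efficacy conclusions are unaffected; what changes is how firmly the trial can speak about vision safety. The change should be made.

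**What to change.** In SAP 7.2 and Tables 5.7 and 5.8, for eyes with both values and separately for worse and contralateral eye (so one eye per patient in each table), add:

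1. The within-eye logMAR change, D42 minus screening, with descriptive statistics including minimum, maximum and 95% CI. The mean alone would not suffice, since gains still offset losses in it.
2. A screening-to-D42 shift table in the SAP's own tenths classes.
3. The number and percentage of eyes with a logMAR loss at or above a size that the sponsor pre-specifies, with the SAP's Wilson CI.
4. A listing of eyes selected on logMAR change. Tenths classes are a poor basis for selection because their steps are unequal: 10/10 to 9/10 is 0.046 logMAR, while 4/10 to 3/10 is 0.125. They also miss losses within the open top class: 16/10 to 11/10 is 0.163 with no change of class.

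State the number of eyes with a screening value but no analysable D42 value beside these results.

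The cost is a few extra outputs from data already collected; SAP Appendix 3 already has a change-from-baseline template. The one drawback is that the listing may include changes within measurement noise, which the choice of threshold can limit.
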